## Jazz Pharmaceuticals, Inc.

## JZP712-201 Statistical Analysis Plan - Protocol Amendment

2

Procedure	Screening (window)	Intervention Period [Days]							EOT (30± 7D after last dose) or E/D	OS telephone call every 3 months	Comments			
		C1		C2		≥ C3								
		D1	D8	D15	D1	D8	D15	D1						
											
 
• D-1 is the calendar day before C1D1.
 
• Screening assessments must be repeated if the first infusion of lorbrena is given outside the stated window.
 
• EOT is defined as 30 days after the last dose of lorbrena, unless the participant starts any subsequent anticancer therapy, in which case the EOT visit should be performed immediately before the start of new therapy.
 
• The EOT assessments will be performed if no recent data are available (ie, within the previous 10 days prior to the EOT visit) or if the last available data show a Grade ≥ 2 increase in AE severity.
 
			
Performance status (ECOG)	X (-7 to -1)	X		X		X		X			-1 day window (except in Cycle 1)			
Single 12-lead ECG	X (-7 to -1)	Repeat if clinically indicated									ECG: cardiac rhythm will be identified in ECG intervals of at least 30 seconds of duration, PR interval, QT interval (raw), heart rate (HR) and QRS complex.			
Highly sensitive serum OR urine pregnancy test (WOCBP only)	X (-7 to -1)	X		X		X		X			Beta subunit-human chorionic gonadotropin (β-hCG) (urine or serum). In WOCBP, if a urine pregnancy test is positive a serum test must be performed and confirmed negative prior to administering IP. See Section 8.4.5 for pregnancy reporting requirements.			
HIV (antibody), Hepatitis B (surface antigen), and Hepatitis C (surface antigen, and RNA if positive by antibody) screening	X (-28 to -1)										All participants will be tested for HIV prior to the enrollment into the study and HIV-positive participants will be excluded from the study. Participants with active hepatitis B (chronic or acute; defined as having a positive HBsAg test result at screening) will be excluded from the study. Participants with past or resolved HBV infection (defined as the presence of HBcAb and absence of HBsAg) are eligible; HBV DNA should be obtained in these participants prior to enrollment. Participants with HCV will be excluded from the study; participants who test positive for HCV antibody are eligible only if PCR is negative for HCV RNA.			

## Jazz Pharmaceuticals, Inc.

## JZP712-201 Statistical Analysis Plan - Protocol Amendment

2

Procedure	Screening (window)	Intervention Period [Days]						EOT (30± 7D after last dose) or E/D	OS telephone call every 3 months	Comments		
		C1		C2		≥ C3						
		D1	D8	D15	D1	D8	D15	D1				
										
 
D-1 is the calendar day before C1D1.
 
Screening assessments must be repeated if the first infusion of lurbinectedin is given outside the stated window.
 
EOT is defined as 30 days after the last dose of lurbinectedin, unless the participant starts any subsequent anticancer therapy, in which case the EOT visit should be performed immediately before the start of new therapy.
 
The EOT assessments will be performed if no recent data are available (ie, within the previous 10 days prior to the EOT visit) or if the last available data show a Grade <math>\geq 2</math> increase in AE severity.
 
		
Coagulation tests	X (-7 to -1)			X			X	X		-3 day window (except in Cycle 1). Clinical laboratory tests are detailed in Appendix 3 .		
Hematology	X (-7 to -1)	X	X	X	X	X	X	X		
-3 day window (except in Cycle 1). Clinical laboratory tests are detailed in Appendix 3. Any participants with febrile neutropenia of any grade, Grade 4 neutropenia, and/or Grade 4 thrombocytopenia, should have relevant tests repeated daily until recovery to Grade <math>\leq 3</math> and through the day after fever resolution, if applicable.
 
For Cycle 3 and after, Hematology and Biochemistry "A" tests on Days 8 and 15 are to be performed only in participants with Grade <math>\geq 3</math> biochemical Grade 4 hematological treatment-related toxicities, or who required dose adjustments due to hematological or biochemical abnormalities in the preceding cycle.
		
Biochemistry-A	X (-7 to -1)		X	X	X	X	X	X		-3 day window (except in Cycle 1). Clinical laboratory tests are detailed in Appendix 3 .		
Biochemistry-B	X (-7 to -1)	X		X			X	X		Albumin, total proteins, Ca ++ and Mg ++ . Total proteins, Ca ++ and Mg ++ will be measured at Screening and repeated thereafter only in those participants with abnormal baseline values. Clinical laboratory tests are detailed in Appendix 3 .		

Note: reference to [Appendix 3](#) corresponds to protocol appendix.

## Jazz Pharmaceuticals, Inc.

## JZP712-201 Statistical Analysis Plan - Protocol Amendment

2

Procedure	Screening (window)	Intervention Period [Days]							EOT (30± 7D after last dose) or E/D	OS telephone call every 3 months	Comments			
		C1		C2		≥ C3								
		D1	D8	D15	D1	D8	D15	D1						
Vital signs (HR, BP, temperature, respiratory rate)	X (-7 to -1)	X		X		X		X			-1 day window (except in Cycle 1)			
											Blood samples will be collected from participants who consent to provide PK samples at the following time points in cycle 1: -1 day before infusion (-5 min).			
AAGP		X									One blood sample for the evaluation of AAGP will be collected at the end of the lorbunectedin infusion (± 5 min) from all participants.			
HRD-positive cohort only: blood sample for confirmation of any pre- identified germline and/or somatic pathogenic mutations	X (-28 to -1)										One blood sample will be collected before lorbunectedin administration in Cycle 1 from all participants in the HRD-positive cohort.			

## Jazz Pharmaceuticals, Inc.

## JZP712-201 Statistical Analysis Plan - Protocol Amendment

2

Procedure	Screening (window)	Intervention Period [Days]							EOT (30± 7D after last dose) or E/D	OS telephone call every 3 months	Comments			
		C1		C2		≥ C3								
		D1	D8	D15	D1	D8	D15	D1						
Blood sample for ctDNA somatic mutational analysis (required)		X									Required sample: the C1D1 sample should be collected before lorbrena administration.			
Blood sample for longitudinal ctDNA somatic mutational analysis (optional)				X		X			X					
Radiological tumor assessment	X (-28 to -1)	Every 6 weeks (±7 days) from the C1D1 for 36 weeks (±7 days). After completion of the Week 36 tumor assessment, every 12 weeks (±14 days) thereafter. The assessments will be performed at these time points until PD, start of a new anticancer therapy, death, EOT visit, or study termination, whichever occurs first.				X (if not performed within 7 days of last treatment evaluation visit for participants who discontinue treatment, see Section 7.1)					Evaluation by contrast enhanced helical CT-scan or MRI, as clinically indicated, of all measurable sites of disease involvement and of all nonmeasurable sites of disease should be done prior to the first Lorbrena administration. While on treatment, evaluation of all original sites of disease involvement should be done per RECIST v1.1. The same initial method must be used throughout the study. For all LCNET of lung participants, CT-scan or MRI of brain will be requested before the planned treatment onset to rule out CNS involvement. Participants showing a response must have a confirmatory assessment at least 4 weeks after initial response. See Appendix 8 for tumor assessment guidelines.			

## Jazz Pharmaceuticals, Inc.

## JZP712-201 Statistical Analysis Plan - Protocol Amendment

2

Procedure	Screening (window)	Intervention Period [Days]							EOT (30± 7D after last dose) or E/D	OS telephone call every 3 months	Comments			
		C1		C2		≥ C3								
		D1	D8	D15	D1	D8	D15	D1						
Pretreatment tumor sample (optional)	X (-28 to -1)	Tumor samples may be submitted at any time during the study.									Pretreatment tumor sample from primary tumor and/or metastasis, either obtained at diagnosis or at any time before the first lurbinectedin administration. Any tumor sample, sample from primary tumor and/or metastasis, (either formalin fixed paraffin-embedded [FFPE] tumor tissue or cytology slides) will be acceptable. Archived tumor samples, if available, can be submitted at any time during the study.			
Administer lurbinectedin		X		X		X					± 3 day window (except in Cycle 1). Refer to criteria for treatment continuation (Section 5.5) and dose delay and reduction rules (Section 6.7) prior to each administration of lurbinectedin.			
On-treatment tumor sample (optional)		Optional biopsy 4 to 6 weeks after C1D1									Optional samples are only obtained from those participants consenting to biomarker analyses via the corresponding option in the ICF.			
OS									X					
AE review		←————→									Adverse events resulting in study discontinuation will be followed until satisfactory resolution per the investigator. See Section 8.4.1.			

## Jazz Pharmaceuticals, Inc.

## JZP712-201 Statistical Analysis Plan - Protocol Amendment

2

Procedure	Screening (window)	Intervention Period [Days]							EOT (30± 7D after last dose) or E/D	OS telephone call every 3 months	Comments			
		C1		C2		≥ C3								
		D1	D8	D15	D1	D8	D15	D1						
												
 
• D-1 is the calendar day before C1D1.
 
• Screening assessments must be repeated if the first infusion of lurbinectedin is given outside the stated window.
 
• EOT is defined as 30 days after the last dose of lurbinectedin, unless the participant starts any subsequent anticancer therapy, in which case the EOT visit should be performed immediately before the start of new therapy.
 
• The EOT assessments will be performed if no recent data are available (ie, within the previous 10 days prior to the EOT visit) or if the last available data show a Grade ≥ 2 increase in AE severity.
 
		
SAE review		↔									All SAEs will be followed until resolution, stabilization, the event is otherwise explained, or the participant is lost to follow-up.  During the OS Follow-up, any spontaneous treatment-related SAEs will be collected and reported.			
Prior/concomitant medications		↔												

Abbreviations: AAGP = alpha-1 acid glycoprotein; AE = adverse event; AP = alkaline phosphatase; ALT = alanine aminotransferase; AST = aspartate aminotransferase; BP = blood pressure; BSA = body surface area; C = cycle; CT = computed tomography; ctDNA = circulating tumor DNA; D = day; ECG = electrocardiogram; E/D = early discontinuation; ECOG = Eastern Cooperative Oncology Group; EOT = end-of-treatment; FFPE = formalin fixed paraffin-embedded; GGT = gamma-glutamyltransferase; HR = heart rate; INR = international normalized ratio; LDH = lactate dehydrogenase; LCNET = large cell neuroendocrine tumor; MRI = magnetic resonance imaging; NA = not applicable; NCI-CTCAE = National Cancer Institute Common Terminology Criteria for Adverse Events; OS = overall survival; PD = progressive disease; PT = prothrombin time; PTT = partial thromboplastin time; RECIST = Response Evaluation Criteria in Solid Tumors; SAE = serious adverse event; ULN = upper limit of normal; WBC = white blood cells.

Jazz Pharmaceuticals, Inc.  
JZP712-201 Statistical Analysis Plan - Protocol Amendment 2

**Appendix 2: NCI CTCAE Criteria v5.0 for Laboratory Parameters**

PARAMETER (SI Unit)	Hypo	Hyper	ATOXGR			
			Grade 1	Grade 2	Grade 3	Grade 4
Hemoglobin (g/L)	Anemia	Hemoglobin increased	Increase in >0 - 2 g/dL	Increase in >2 - 4 g/dL	Increase in >4 g/dL	~
			Hemoglobin (Hgb) <LLN - 10.0 g/dL; <LLN - 6.2 mmol/L; <LLN - 100 g/L	Hgb <10.0 - 8.0 g/dL; <6.2 - 4.9 mmol/L; <100 - 80 g/L	Hgb <8.0 g/dL; <4.9 mmol/L; <80 g/L	~
Platelets (10  /L)	Platelet count decreased		<LLN - 75,000/mm  ; <LLN - 75.0 × 10  /L	<75,000 - 50,000/mm  ; <75.0 - 50.0 × 10  /L	<50,000 - 25,000/mm  ; <50.0 - 25.0 × 10  /L	<25,000/mm  ; <25.0 × 10  /L
Leukocytes (10  /L)	White blood cell decreased		<LLN - 3000/mm  ; <LLN - 3.0 × 10  /L	<3000 - 2000/mm  ; <3.0 - 2.0 × 10  /L	<2000 - 1000/mm  ; <2.0 - 1.0 × 10  /L	<1000/mm  ; <1.0 × 10  /L
Neutrophils (10  /L)	Neutrophil count decreased		<LLN - 1500/mm  ; <LLN - 1.5 × 10  /L	<1500 - 1000/mm  ; <1.5 - 1.0 × 10  /L	<1000 - 500/mm  ; <1.0 - 0.5 × 10  /L	<500/mm  ; <0.5 × 10  /L
Lymphocytes (10  /L)	Lymphocyte count decreased	Lymphocyte count increased	<LLN - 800/mm  ; <LLN - 0.8 × 10  /L	<800 - 500/mm  ; <0.8 - 0.5 × 10  /L	<500 - 200/mm  ; <0.5 - 0.2 × 10  /L	<200/mm  ; <0.2 × 10  /L
			~	>4000/mm  - 20,000/mm 	>20,000/mm 	~
Eosinophils (%)		Eosinophilia	>ULN and >Baseline	-	Steroids initiated	-
Activated Partial Thromboplastin Time (s)		Activated partial thromboplastin time prolonged	>ULN - 1.5 × ULN	>1.5 - 2.5 × ULN	>2.5 × ULN; bleeding	~
International Normalized Ratio		INR increased	>1.2 - 1.5	>1.5 - 2.5	>2.5	~

Jazz Pharmaceuticals, Inc.

JZP712-201 Statistical Analysis Plan - Protocol Amendment 2

PARAMETER (SI Unit)	Hypo	Hyper	ATOXGR			
			Grade 1	Grade 2	Grade 3	Grade 4
Albumin (g/L)	Hypoalbuminemia		<LLN - 3 g/dL; <LLN - 30 g/L	<3 - 2 g/dL; <30 - 20 g/L	<2 g/dL; <20 g/L	~
Glucose (mmol/L)	Hypoglycemia		<LLN - 55 mg/dL; <LLN - 3.0 mmol/L	<55 - 40 mg/dL; <3.0 - 2.2 mmol/L	<40 - 30 mg/dL; <2.2 - 1.7 mmol/L	<30 mg/dL; <1.7 mmol/L
Creatinine (umol/L)		Creatinine increased	>ULN - 1.5 × ULN	>1.5 - 3.0 × baseline if baseline was abnormal; >1.5 - 3.0 × ULN if baseline was normal	>3.0 × baseline-6.0 × ULN if baseline was abnormal; >3.0 - 6.0 × ULN if baseline is normal	>6.0 × ULN
Creatine phosphokinase (IU/L)		CPK increased	>ULN - 2.5 × ULN	>2.5 × ULN- 5 × ULN	>5.0 X ULN - 10.0 x ULN	>10.0 × ULN
Alkaline Phosphatase (uKat/L)		Alkaline phosphatase increased	>ULN - 2.5 × ULN if baseline was normal; 2.0 - 2.5 × baseline if baseline was abnormal	>2.5 - 5.0 × ULN if baseline was normal; >2.5 - 5.0 × baseline if baseline was abnormal	>5.0 - 20.0 × ULN if baseline was normal; >5.0 - 20.0 x baseline if baseline was abnormal	>20.0 × ULN if baseline was normal; >20.0 x baseline if baseline was abnormal
Aspartate Aminotransferase (uKat/L)		Aspartate aminotransferase increased	>ULN - 3.0 × ULN if baseline was normal; 1.5 - 3.0 × baseline if baseline was abnormal	>3.0 - 5.0 × ULN if baseline was normal; >3.0 - 5.0 × baseline if baseline was abnormal	>5.0 - 20.0 × ULN if baseline was normal; >5.0 - 20.0 x baseline if baseline was abnormal	>20.0 × ULN if baseline was normal; >20.0 x baseline if baseline was abnormal
Alanine Aminotransferase (uKat/L)		Alanine aminotransferase increased	>ULN - 3.0 × ULN if baseline was normal; 1.5 - 3.0 × baseline if baseline was abnormal	>3.0 - 5.0 x ULN if baseline was normal; >3.0 - 5.0 × baseline if baseline was abnormal	>5.0 - 20.0 × ULN if baseline was normal; >5.0 - 20.0 x baseline if baseline was abnormal	>20.0 × ULN if baseline was normal; >20.0 x baseline if baseline was abnormal

Jazz Pharmaceuticals, Inc.

JZP712-201 Statistical Analysis Plan - Protocol Amendment 2

PARAMETER (SI Unit)	Hypo	Hyper	ATOXGR			
			Grade 1	Grade 2	Grade 3	Grade 4
Serum Calcium (mmol/L)	Hypocalcemia	Hypercalcemia	>ULN - 2.9 mmol/L	>2.9 - 3.1 mmol/L	>3.1 - 3.4 mmol/L	>3.4 mmol/L
			<LLN - 2.0 mmol/L	<2.0 - 1.75 mmol/L	<1.75 - 1.5 mmol/L	<1.5 mmol/L
Magnesium (mmol/L)	Hypomagnesemia	Hypermagnesemia	>ULN - 3.0 mg/dL; >ULN - 1.23 mmol/L	~	>3.0 - 8.0 mg/dL; >1.23 - 3.30 mmol/L	>8.0 mg/dL; >3.30 mmol/L
			<LLN - 1.2 mg/dL; <LLN - 0.5 mmol/L	<1.2 - 0.9 mg/dL; <0.5 - 0.4 mmol/L	<0.9 - 0.7 mg/dL; <0.4 - 0.3 mmol/L	<0.7 mg/dL; <0.3 mmol/L
Potassium (mmol/L)	Hypokalemia	Hyperkalemia	>ULN - 5.5 mmol/L	>5.5 - 6.0 mmol/L	>6.0 - 7.0 mmol/L	>7.0 mmol/L
			<LLN - 3.0 mmol/L	~	<3.0 - 2.5 mmol/L	<2.5 mmol/L
Sodium (mmol/L)	Hyponatremia	Hypernatremia	>ULN - 150 mmol/L	>150 - 155 mmol/L	>155 - 160 mmol/L	>160 mmol/L
			<LLN - 130 mmol/L	125-129 mmol/L	120-124 mmol/L	<120 mmol/L
Bilirubin (umol/L)		Blood bilirubin increased	>ULN - 1.5 x ULN if baseline was normal; > 1.0 - 1.5 x baseline if baseline was abnormal	>1.5 - 3.0 x ULN if baseline was normal; >1.5 - 3.0 x baseline if baseline was abnormal	>3.0 - 10.0 x ULN if baseline was normal; >3.0 - 10.0 x baseline if baseline was abnormal	>10.0 x ULN if baseline was normal; >10.0 x baseline if baseline was abnormal
Urinary protein		Proteinuria	1+ proteinuria; urinary protein $\geq$ ULN - <1.0 g/24 hrs	2+ and 3+ proteinuria; urinary protein 1.0- <3.5g/24hrs	4+ proteinuria; urinary protein $\geq$ 3.5g/24hrs	~

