6.10.1. Allowed Concomitant Medications

The following medications are allowed during study participation:

- Colony-stimulating factors such as G-CSF or GM-CSF
 - Primary G-CSF or GM-CSF is mandated during the first and all subsequent cycles. The type, dose, and scheme to be used may vary according to institutional/standard practices or guidelines. A mandatory window of at least 24 hours and up to 72 hours must be allowed from the last dose of study intervention administration until G-CSF or GM-CSF prophylaxis is started.
- Therapies for pre-existing and treatment-emergent medical conditions, including pain management
- Blood products and transfusions, as clinically indicated
- Bisphosphonates
- Primary and secondary prophylaxis and/or symptomatic treatment for emesis according to ASCO guidelines for nausea or vomiting (see [Section 6.6; Hesketh, 2017](#))
- Erythropoietin treatment according to ASCO guidelines
- Anticoagulation therapy.

In addition to the above, all treatments that the Investigator considers necessary for a participant's welfare may be administered at the discretion of the Investigator in keeping with the

community standards of medical care. All concomitant medication will be recorded in the case eCRF including all prescription, OTC, herbal supplements, and IV medications and fluids. If changes occur during the trial period, documentation of the medication as per [Section 6.10](#) may also be included in the eCRF.

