## Jazz Pharmaceuticals, Inc.

## JZP712-201 Statistical Analysis Plan - Protocol Amendment

2

Other Screening tests	Serology (HIV antibody, HBsAg, and hepatitis C virus antibody)
-----------------------	--

ALT=alanine aminotransferase; AP=alkaline phosphokinase; AST=aspartate aminotransferase; CPK=creatinine phosphokinase; GGT=gamma-glutamyl transferase; HBcAb=hepatitis B core antibody; HBsAg=hepatitis B surface antigen; hCG=human chorionic gonadotropin; HCV=hepatitis C virus; HIV=human immunodeficiency virus; LDH=lactate dehydrogenase; PT=prothrombin time; PTT=partial thromboplastin time; ULN=upper limit of normal.

For all hematology, coagulation and biochemistry tests, the laboratory values at baseline and each of the post-baseline assessments until EOT visit will be summarized and presented using descriptive statistics, along with the number and percentage of participants with tests not done.

For each of the post-baseline assessments, change between baseline and that assessment in a specific laboratory value will be calculated as follows,

Change in lab value = [Lab value at the post-baseline assessment] – [Lab value at baseline], and will be summarized and presented using descriptive statistics.

If the laboratory value is not done or missing at either baseline or a specific post-baseline assessment for a participant, change between baseline and that assessment will be treated as unknown. For each of the post-baseline assessments, the number and percentage of participants with unknown changes between baseline and that assessment will also be presented.

The non-protocol specified tests (if any reported), and urinalysis results will not be summarized; they will only be included in by-participant listings.

Data recorded by the laboratory will be converted to the International System of Units (SI) and summary tables will be generated using both SI and Conventional units.

Quantitative laboratory measurements reported as “< X”, i.e., below the lower limit of quantification (LLQ), or “> X”, i.e., above the upper limit of quantification (ULQ), will be converted to X for the purpose of quantitative summaries, but will be presented as recorded, i.e., as “< X” or “> X” in the listings.

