Clinical laboratory results will be graded according to CTCAE criteria, CTCAE v5.0 criteria (Appendix 2). The frequency and percentage of participants with each CTCAE grade for each visit during the treatment period will be described by cohort. Both the scheduled and unscheduled assessments will be used to identify the worst post-baseline values.

Listings of all laboratory data with results reported using SI and Conventional units, normal reference ranges, and CTCAE grades (when possible) will be provided using Safety analysis set.

Pregnancy test results and other screening tests will be included in by-participant listings only.

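### SAP Appendix 2 grades INR on absolute cut-offs only, so a participant already on a permitted INR-raising anticoagulant is tabulated as laboratory Grade 2 or 3 with no change from baseline

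*SAP*

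**What the plan says.** SAP Appendix 2, row "International Normalized Ratio", grades a rise only: above 1.2 up to 1.5 is Grade 1, above 1.5 up to 2.5 is Grade 2, and above 2.5 is Grade 3. No Grade 4 is defined. Neither the participant's baseline nor anticoagulant use enters the row. In the same table, the rows for creatinine, alkaline phosphatase, AST, ALT and bilirubin carry baseline-relative limits; the creatinine and aminotransferase rows, for instance, contain "1.5 - 3.0 × baseline if baseline was abnormal".

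Protocol 6.10.1 lists "Anticoagulation therapy" among the allowed medications and attaches no INR limit. The eligibility criteria (protocol 5.1 and 5.2) and the retreatment criteria (protocol Table 4) set none either.

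SAP 10.3 makes Appendix 2 the grading source, and PT/INR is in its Table 6. On the grade summary it says: "The frequency and percentage of participants with each CTCAE grade for each visit during the treatment period will be described by cohort". It plans no table of shift from baseline grade. For the continuous values it plans more: "For all hematology, coagulation and biochemistry tests, the laboratory values at baseline and each of the post-baseline assessments until EOT visit" are to be summarised, together with the change from baseline.

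The row "Coagulation tests" in SAP Appendix 1 appears to place the test at screening, Day 1 of Cycle 2, Day 1 of later cycles and end of treatment, with no Day 8 or Day 15 sample.

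**The concern.** An INR-raising anticoagulant is given to raise the INR. A participant who enters on one has a raised value before the first dose of lurbinectedin. Under fixed cut-offs that value gets a grade, and a by-visit grade table without a shift presents it in the same cell as a rise that began on treatment. SAP 7.2.2 defines the treatment period as first to last dose, and coagulation is first tested at screening, so the specified grade table need not show the pre-treatment grade at all.

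At stake is the readability of one safety table in small cohorts. With 12 to 20 participants, one or two such people can make up a noticeable part of the Grade 2-3 INR counts, and the table alone would not show that their values were there from the start.

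**Working it through.** The plan gives no figure of its own on this point, so there is none to reproduce. The check applies the printed cut-offs to plausible values.

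**Inputs from the documents.** INR bands from SAP Appendix 2; initial cohort sizes of 12 and 20 from protocol 9.2; baseline as the latest non-missing value on or before first dose (SAP 7.2.1).

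**Assumptions, not in the documents.** A target INR of 2.0-3.0, with 1.5-2.0 and 2.5-3.5 as alternatives, and 0-10% of participants on an anticoagulant that raises INR.

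**Step 1: grade by the printed row.** Grade = 3 if INR > 2.5; 2 if > 1.5; 1 if > 1.2; otherwise 0.

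- Target 2.0-3.0: every value is Grade 2 or 3. The split falls at 2.5, so (2.5 - 2.0)/(3.0 - 2.0) = half the width of the range is Grade 2 and half is Grade 3. This describes the range, not how participants' values would be distributed.
- Target 1.5-2.0: every value above 1.5 is Grade 2.
- Target 2.5-3.5: every value above 2.5 is Grade 3.

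The finding therefore needs only an INR above 1.5, not one particular target.

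**Step 2: compare with a baseline-relative rule.** For illustration, take ratio = on-study INR / baseline INR, with Grade 1 above 1 to 1.5, Grade 2 above 1.5 to 2.5 and Grade 3 above 2.5. These multiples are not in the documents.

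| Baseline INR | On-study INR | Printed grade | Ratio | Relative grade |
|---|---|---|---|---|
| 2.0 | 2.0 / 2.5 / 3.0 | 2 / 2 / 3 | 1.00 / 1.25 / 1.50 | 0 / 1 / 1 |
| 2.5 | 2.0 / 2.5 / 3.0 | 2 / 2 / 3 | 0.80 / 1.00 / 1.20 | 0 / 0 / 1 |
| 3.0 | 2.0 / 2.5 / 3.0 | 2 / 2 / 3 | 0.67 / 0.83 / 1.00 | 0 / 0 / 0 |
| 1.0 (drug started on study) | 2.0 / 2.5 / 3.0 | 2 / 2 / 3 | 2.00 / 2.50 / 3.00 | 2 / 2 / 3 |

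The first three rows show that the printed grade does not respond to the starting value. The last row shows the limit of the remedy: for someone who starts from a normal INR on study, baseline multiples give the same grades as the printed limits.

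**Step 3: size per participant.** In a cohort of 20, one affected participant adds 1/20 = 5 percentage points to the Grade 2-3 count at a visit, and two add 2/20 = 10. In a cohort of 12, one adds 1/12 = 8.3. Under the assumed 0-10% use, the artefact in a cohort of 20 is 0 to 10 percentage points, so it may be nil.

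**The case against.** The case against has real force, and most of it limits the point without removing it.

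- **These are not adverse events.** A reader might infer that such participants are reported with coagulation toxicity. The documents do not support that. Appendix 2 produces derived laboratory grades. Under protocol 8.3.4 and Appendix 4 an abnormal result becomes an adverse event only if the investigator judges it clinically significant. The secondary safety endpoint is AEs and SAEs. INR is not in the retreatment criteria (protocol Table 4), not named among the dose-reduction triggers (protocol 6.7) and not part of the futility rules (protocol 9.5, SAP 5.5).
- **A true rise can still be found.** A reader might infer that an INR rise from hepatotoxicity, a risk named in protocol 2.3.1, would be indistinguishable from drug effect. It would not. SAP 10.3 plans change from baseline and full listings with grades, SAP 8.4 has baseline coagulation results reported with the safety tables, SAP 8.9 lists concomitant medications by participant, and the liver tests are graded separately with baseline clauses. These offset the fault but do not correct the grade counts: the change summary is aggregate and cannot show which Grade 2-3 entries were present before treatment.
- **Not every visit is affected.** Coagulation is tested only at some visits. The end-of-treatment sample falls after the last dose, so on the SAP 7.2.2 definition it may lie outside the by-visit grade table.
- **INR is not alone.** Many rows have no baseline clause, among them aPTT, platelets, neutrophils, CPK and the electrolytes. The absence of a clause is therefore not an inconsistency in itself. The reason to single out INR is that a permitted drug class can raise it on purpose.
- **The size is assumed.** Neither the target INR nor the share of users is in the documents, and protocol 6.10.1 names no class of anticoagulant. That Grade 3 INR counts would be wholly artefactual is conjecture.

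**Conclusion.** The point holds in limited form. Followed as written, the plan shows a participant who is on an INR-raising anticoagulant at baseline, with INR staying above 1.5, as laboratory Grade 2 or 3 at each tabulated visit with a coagulation test, whether or not the value has moved. This follows from the printed cut-offs and does not depend on the assumed 2.0-3.0 target.

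The consequence is confined to the INR grade summary. The primary endpoint, the adverse event endpoint and the cohort decisions are untouched. The increment per affected participant is exact (5 percentage points in 20, 8.3 in 12), but their number is unknown and could be zero. The change is worth making because the table would otherwise mislead and the repair is cheap, not because a trial conclusion hangs on it.

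**What to change.** In SAP Appendix 2 and 10.3:

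1. Check the INR row against the CTCAE v5.0 source in the SAP's reference list, since Appendix 2 carries that title, and take any baseline-relative limits from there. The multiples in the illustration above are not a proposal for the final wording.
2. For participants on an anticoagulant at baseline, identified from the coded concomitant-medication data (SAP 8.9), grade INR relative to baseline. Keep the printed limits for everyone else.
3. Flag or footnote participants who start an anticoagulant on study, with their number per cohort, because baseline multiples do not remove the drug effect for them. The same flag would help a reader of the aPTT row.
4. Add a baseline-to-worst grade shift for INR. SAP 10.3 already provides for finding the worst post-baseline value from scheduled and unscheduled tests.

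The cost is one table row, one merge, one footnote and one shift table. No new data are needed: protocol 6.10 already requires start and end dates, and the medications are coded to ATC level 4 and preferred term. The small downside is reliance on correct anticoagulant dates. SAP 7.4.4 sets a missing start day to the first of the month and a missing month to January, and leaves a start date with no year unimputed. An on-study start could thus be misread as baseline use, so the SAP should say how such records are classified.
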